[*The site Principal Investigator should sign and date at the indicated location below. A written signature/date is acceptable (e.g., scanned and sent via email as a PDF version). An electronic signature is also acceptable (e.g., sent via email as a PDF version).]	
<hr/> Site Principal Investigator (Print)	
<hr/> Site Principal Investigator (Signature)	<hr/> Date

Protocol Synopsis

Title	Elotuzumab in IgG4-Related Disease
Clinical Phase	II
Number of Sites	Part 1: approximately 3 Part 2: approximately 10
IND Sponsor/Number	DAIT/NIAID, NIH / IND# 147042
Study Objectives	
Primary Objectives
 
Part 1: To determine the safety and tolerability of the addition of elotuzumab to prednisone in participants with IgG4-RD.
 
Part 2: To compare the effect of the addition of elotuzumab versus placebo to prednisone on the IgG4-RD RI at 48 weeks in participants with IgG4-RD.
 
Secondary Objectives
 
 1. To compare the effect of the addition of elotuzumab versus placebo to prednisone on complete remission at 48 weeks. 2. To compare the effect of the addition of elotuzumab versus placebo to prednisone on the number of disease flares (as defined in Section 3.5.3) per participant over time. 3. To compare the effect of the addition of elotuzumab versus placebo to prednisone on the change from baseline in Physician Global Assessment (PhGA) at 4, 8, 12, 16, 20, 24, 28, 32, 36, 40, 44 and 48 weeks. 4. To compare the effect of the addition of elotuzumab versus placebo to prednisone on Patient Global Assessment (PGA) at 4, 8, 12, 16, 20, 24, 28, 32, 36, 40, 44, and 48 weeks. 5. To compare the effect of the addition of elotuzumab versus placebo to prednisone on safety. 
Exploratory Objectives
 
 1. To compare the effect of the addition of elotuzumab versus placebo to prednisone on serum immunoglobulin levels, IgG subclass concentrations, IgE levels, eosinophils, and serum C3 and C4 levels.

	
2. To compare the effect of the addition of elotuzumab versus placebo to prednisone on participants' ELF scores.3. To evaluate the effect of elotuzumab on CD4+ T cells and B cell subsets, specifically:
a. CD4+ cytotoxic T lymphocytesb. CD8+ cytotoxic T lymphocytesc. CD4+ T follicular helper cellsd. CD4+ peripheral helper T cellse. Plasmablastsf. Activated B cells, including double-negative (CD19+IgD-CD27-) B cells4. To determine the kinetics of cell depletion induced by elotuzumab on disease-associated, SLAMF7-expressing lymphocyte subpopulations including CD4+ cytotoxic T cells and activated B cells, including plasmablasts.5. To determine the effect of elotuzumab at the tissue level, using submandibular gland biopsies in participants with submandibular gland disease who consent separately to biopsies before and after treatment.6. To determine the utility of using the clonally-expanded effector subset (CD57+CD28-) of CD4+CTLs as a biomarker of disease activity.7. To determine the utility of soluble plasma SLAMF7 levels as indicators of disease activity and predictors of disease relapse.8. To evaluate the longitudinal profile of patient reported outcomes on quality of life over the study period using the SF-36 health survey.
Study Design	This is a two-part multi-center clinical trial in participants with active IgG4-RD. Part 1 is an open-label, dose escalation phase to determine the safety of elotuzumab for investigation in IgG4-RD. If the addition of elotuzumab to prednisone is determined to be safe, Part 2 will be initiated as randomized, placebo-controlled, double-blinded trial. Part 2 will compare the effects of the addition of elotuzumab versus placebo to prednisone in participants with IgG4-RD. Approximately 75 participants with active IgG4-RD will be enrolled in the overall program, 12 in Part 1 and 63 in Part 2.
Primary Endpoint	Part 1: Primary Safety Endpoint The proportion of participants in each cohort who experience at least one Grade 3 or higher adverse event during study participation. Part 2: Primary Efficacy Endpoint Disease response at 48 weeks, defined as percent improvement in the IgG4-RD RI score over baseline.

Secondary Endpoints	
Part 2: Key Secondary Efficacy Endpoint
 
 1. Complete remission at 48 weeks, defined as an IgG4-RD RI Score of 0 and a glucocorticoid dose of 0 mg/day and no flare since beginning treatment. 
Part 1 and Part 2: Additional Secondary Efficacy Endpoints
 
 1. The proportion of participants that reach the following threshold levels of IgG4-RD RI improvement at 48 weeks: 50% and 75%. 2. Number of disease flares, as defined in Section 3.5.3, by 24 and 48 weeks. 3. Change in PhGA from baseline. 4. Change in PGA from baseline. 5. Disease-related damage, as measured by the damage section of the IgG4-RD RI at 24 weeks. 
Part 1 and Part 2: Secondary Safety Endpoints
 
 1. The proportion of participants who experience at least one Grade 2 or higher adverse event. 2. The proportion of participants with a Grade 3 or higher infection. 3. The proportion of participants who experience a malignancy. 4. The proportion of participants who experience a Hepatotoxicity, defined as an increase in the aspartate aminotransferase (AST) or alanine aminotransferase (ALT) to elevations three times the upper limit of normal. 5. The proportion of participants who experience a serious adverse event. 6. The proportion of participants who experience infusion reactions, defined as any adverse reaction within 24 hours of infusion which are Grade 2 or higher events and at least possibly related to study drug. 
Part 2: Secondary Safety Endpoint
 
 1. The proportion of participants who experience at least one Grade 3 or higher adverse event.
Exploratory Endpoints	
Part 1 and 2: Exploratory Endpoints
 
 1. Serum immunoglobulin levels, IgG subclass concentrations, IgE levels, eosinophils, and serum C3 and C4 levels. 2. ELF score (see Section 3.5.7). 3. Blood concentrations of T cells and B cell subsets of interest, specifically: 
 a. CD4+ cytotoxic T lymphocytes b. CD8+ cytotoxic T lymphocytes c. CD4+ T follicular helper cells

	
d. CD4+ peripheral helper T cells
 
e. Plasmablasts
 
f. Activated B cells, including double-negative (CD19+IgD-CD27-) B cells
 
4. Comparison of the kinetics of cell depletion induced by the addition of elotuzumab versus placebo to prednisone on disease-associated, SLAMF7-expressing lymphocyte subpopulations, including CD4+ cytotoxic T cells and activated B cells, including plasmablasts.
 
5. Comparison of elotuzumab and placebo with regard to the impact of the tissue concentrations of CD4+ cytotoxic T cells and activated B cells subsets of interest, pre- and post-treatment submandibular gland biopsies.
 
6. Correlation of the clonally-expanded effector subset (CD57+CD28-) of CD4+CTLs with disease activity.
 
7. Correlation of soluble plasma SLAMF7 levels with disease activity and risk of relapse.
 
8. SF-36 health survey.

Accrual Objective	Approximately 75 participants will be enrolled in the overall program, 12 in Part 1 and 63 in Part 2.
Study Duration	
The rate of recruitment to AIG01 is anticipated to be 0.5 participants per week.
 
 • The duration target for Part 1A prior to initiation of Part 1B is 21 weeks (12 weeks of recruitment, 9 weeks of follow-up). • The duration target for Part 1B prior to initiation of Part 2 is 60 weeks (12 weeks of recruitment, 48 weeks of follow-up). • The duration target for Part 2 is 176 weeks (128 weeks of recruitment, 48 weeks of follow-up). 
The total study duration is estimated to be 257 weeks (approximately 5 years).

Treatment Description	
Part 1
 
Elotuzumab
 
Participants receive either a 1-month or twelve-month regimen of elotuzumab, depending on enrollment phase (see Study Design Section 3). Each intravenous dose will be 10 mg/kg, to be determined based on participant's weight. Rounding is permissible within 5% of the nominal dose. The participant's actual weight will be used for dosing. At the Baseline/Day 0 visit, the participant's screening weight will be used for calculation of the Baseline/Day 0 infusion dose. For all subsequent infusions, weight from the previous visit may be used unless weight was

	
obtained more than 42 days previously. If more than 42 days have elapsed since the previous visit, the participant's current weight should be used for calculation.
 
The 1-month regimen consists of 4 weekly doses of elotuzumab (10 mg/kg) on days 0, 7, 14, and 21. The twelve-month regimen consists of 6 doses at Baseline/Day 0, Week 8, Week 16, Week 24, Week 32, and Week 40.
 
Prednisone
 
Participants will receive a standardized prednisone taper, starting at either 40 mg orally daily or 30 mg orally daily based on doses received during the screening period. This will be tapered to discontinuation over a 10-week period.
 
Part 2
 
Participants receive either elotuzumab or placebo for elotuzumab in a 2:1 ratio.
 
Elotuzumab/Placebo
 
It is anticipated that the twelve-month regimen from Part 1 will be used for the elotuzumab and placebo for elotuzumab dosing schedule, provided there is no safety signal detected. The pharmacist is the only site personnel not blinded to the treatment assignment. Placebo for elotuzumab will be investigational sites' stocked 0.9% normal saline prepared by the site pharmacist.
 
Prednisone
 
Participants will receive the same standard prednisone taper as described in Part 1.

Inclusion Criteria	
1. Participant must be able to understand and provide informed consent and be willing to comply with study procedures and follow up.2. Are at least 18 years of age and not older than 70 years of age at screening.3. Meet the ACR/EULAR Classification Criteria for IgG4-RD.4. Have active disease based at screening on an IgG4-RD RI ≥ 4, with disease manifestations in at least two organ systems.5. May have newly-diagnosed or relapsing disease at screening. Relapsing disease is defined as IgG4-RD that has previously been in remission but is now active again.6. May be on treatment or off treatment at the time of screening. If on treatment, must be willing to discontinue those other treatments before the baseline visit.

	
7. No history of severe allergic reactions to monoclonal antibodies.8. Female participants of childbearing potential must have a negative pregnancy test upon study entry.9. Female participants of childbearing potential and male participants with a partner of childbearing potential must agree to consistently and correctly use FDA approved highly effective methods of birth control, as shown in Appendix 8: Acceptable Contraception Methods for Females of Reproductive Potential, for the entire duration of the study and 6 months after last elotuzumab infusion.10. Immunization with one of the FDA authorized or licensed SARS-CoV-2 vaccines as per CDC recommendations at the time of informed consent is required for study entry. Vaccination series must have been completed at least 2 weeks prior to start of study therapy.
Exclusion Criteria	
1. Presence of a condition other than IgG4-RD that (e.g., asthma) is likely to require systemic Glucocorticoids (GC) for disease control during the period of the trial.2. Malignancy within 5 years (except successfully treated in situ cervical cancer, resected squamous cell or basal cell carcinoma of the skin.)3. The following lab values as indicators of hepatic dysfunction:
a. Serum aspartate aminotransferase (AST) or alanine aminotransferase (ALT) greater than three times the upper limit of normal (ULN)b. Total bilirubin > two times the ULN unless caused by Gilbert's disease. Gilbert's disease with total bilirubin > three times ULN.c. Serum albumin < 2.5 gm/dL.4. Evidence of another uncontrolled condition which, in the judgment of the investigator, could interfere with participation in the trial according to the protocol.5. Active infection requiring hospitalization or treatment with systemic antimicrobial agents within the 30 days prior to treatment allocation/randomization.6. Prior use of rituximab or other B cell depleting agents within 9 months of enrollment unless B cells have been demonstrated to have repopulated.7. Use of any investigational agent or biologic and non-biologic DMARDS within 5 half-lives of the agent (or 6 months if the half-life is unknown) prior to enrollment.8. Any of the following laboratory tests at the Screening Visit:
a. White blood cell (WBC) count < $3.0 \times 10^3/\mu\text{L}$.b. Absolute neutrophil count (ANC) < $1.5 \times 10^3/\mu\text{L}$.c. Hemoglobin < 10 g/dL.d. Platelet count < $75 \times 10^9/\text{L}$.

	
e. Estimated glomerular filtration rate (eGFR) ≤ 45 ml/minute/1.73m².9. The use of supplemental oxygen at baseline.10. At or within 90 days of screening: Positive Interferon-Gamma Release Assay (IGRA). Indeterminate IGRA must be repeated (with same or other IGRA per local policy) and shown to be negative. Alternatively, if the assay remains indeterminate, a participant must have a negative PPD. Finally, if the participant has had the Bacille Calmette-Guerin (BCG) vaccine or has some other condition complicating the interpretation of TB testing, consultation with infectious disease specialist must be obtained before receipt of the first investigational infusion.
a. Participants diagnosed with latent TB are eligible but must have received appropriate prophylaxis for 30 days before their first investigational infusion.11. Medical history or serologic evidence at Screening of chronic infections including:
a. Human immunodeficiency virus infection.b. Hepatitis B as indicated by surface antigen or hepatitis B core antibody positivityc. Hepatitis C as indicated by anti-hepatitis C antibody positivity; if a participant is Hepatitis C antibody positive, they will be eligible to participate in the study if he/she is negative for viral load at Screening.12. Live vaccines within 8 weeks of initiating study therapy.13. Participant is pregnant or breastfeeding, or planning a pregnancy while enrolled in the study.14. Substance use disorder, including the recurrent use of alcohol and/or drugs within the past year associated with clinically significant impairment associated with failure to meet major responsibilities at work, school, or home.15. IgG4-RD that is dominated primarily by advanced fibrotic lesions. Specifically, participants whose disease manifestations consist only of
a. retroperitoneal fibrosis,b. fibrosing mediastinitis,c. sclerosing mesenteritis, andd. Riedel's thyroiditis.Participants with these disease manifestations can be included, however, only if they have disease in 2 organ systems that is not of an advanced fibrotic nature and otherwise meet the Inclusion and Exclusion Criteria.16. Evidence a SARS-CoV-2 (COVID-19) infection started within the 30 days prior to treatment allocation/randomization. Participants
--	--

	
diagnosed with SARS-CoV-2 (COVID-19) infection more than 30 days prior to treatment allocation/randomization must have symptoms resolved and be deemed fit to participate in the trial.

Safety Stopping Guidance	
The following events will trigger an ad hoc DSMB review (Section 12.11.3):
 
• Any death that is at least possibly related to elotuzumab, IgG4-RD, or a study-mandated procedure;• Any grade 4 adverse event, including infection, that is a clinical event such as a sign/symptom, diagnosis, or laboratory abnormality with clinical consequence and at least possibly related to use of the investigational study medication. Any life-threatening infusion reactions during infusion of study treatment or within the two-hour observation period after study treatment that lead to permanent discontinuation of the infusion, including anaphylaxis;• Two or more of the first 6 treated participants within a given cohort (cohorts 1a, 1b or 2) experience a drug-related adverse event resulting in the permanent discontinuation of study treatment; subsequently, if >20% of participants on study or within a cohort experience a drug-related adverse event resulting in the permanent discontinuation of study treatment;• The occurrence of a Grade 3 or higher related and unexpected SAE in three or more of the study participants who have received a study treatment;• Malignancy• Any event which in the opinion of the Protocol Chair or Medical Monitor merits DSMB review. 
Events that trigger an ad hoc DSMB review will be cumulative over Parts 1 and 2 of the study.

Table of Contents

1	Background and Rationale	19
1.1	Background and Scientific Rationale.....	19
1.1.1	IgG4-Related Disease (IgG4-RD).....	19
1.1.2	Current Treatment of IgG4-RD and Rationale for the Clinical Study	19
1.2	Rationale for Selection of Investigational Product or Intervention.....	20
1.3	Preclinical Experience	22
1.4	Rationale for Study Population	23
1.5	Clinical Studies	23
1.5.1	Rationale for Elotuzumab Dosing Schedule Change following Part 1A of Protocol AIG01.....	25
2	Study Hypotheses/Objectives	26
2.1	Hypotheses.....	26
2.2	Mechanistic Hypotheses.....	27
2.3	Primary Objectives.....	27
2.4	Secondary Objectives.....	27
2.5	Exploratory Objectives.....	27
3	Study Design.....	28
3.1	Description of Study Design	28
3.1.1	Part 1: Open-label Phase.....	28
3.1.2	Transition to Part 2	30
3.1.3	Part 2: Randomized Phase	30
3.1.4	Study Duration	31
3.2	Primary Endpoints.....	32

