3.3 Secondary Endpoints

Part 2: Key Secondary Efficacy Endpoint

1. Complete remission at 48 weeks, defined as an IgG4-RD RI Score of 0 and a glucocorticoid dose of 0 mg/day and no flare since beginning treatment.

Part 1 and Part 2: Additional Secondary Efficacy Endpoints

1. The proportion of participants that reach the following threshold levels of IgG4-RD RI improvement at 48 weeks: 50% and 75%.
2. Number of disease flares, as defined in Section 3.5.3.
3. Change in PhGA from baseline.
4. Change in PGA from baseline.
5. Disease-related damage, as measured by the damage section of the IgG4-RD RI.

Part 1 and Part 2: Secondary Safety Endpoints

1. The proportion of participants who experience at least one Grade 2 or higher adverse event.
2. The proportion of participants with a Grade 3 or higher infection.
3. The proportion of participants who experience a malignancy.
4. The proportion of participants who experience a Hepatotoxicity, defined as increase in the aspartate aminotransferase (AST) or alanine aminotransferase (ALT) to elevations three times the upper limit of normal.
5. The proportion of participants who experience a serious adverse event.
6. The proportion of participants who experience infusion reactions, defined as any adverse reaction within 24 hours of infusion which are Grade 2 or higher events and at least possibly related to study drug.

Part 2: Secondary Safety Endpoint

1. The proportion of participants who experience at least one Grade 3 or higher adverse event.

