3.5.2 IgG4-RD Responder Index

The IgG4-RD RI is based on the Birmingham Vasculitis Activity Score for Wegener's Granulomatosis [32], utilized for the evaluation and licensure of rituximab in antineutrophil cytoplasmic antibody (ANCA)-associated vasculitis [33]. The IgG4-RD RI detects change in disease activity and identifies improvements and worsening in the same or different organ systems. The IgG4-RD RI has been used in prior clinical trials to monitor IgG4-RD disease activity [11, 18, 34].

During Part 1A, disease activity will be measured by the IgG4-RD RI at Screening, Baseline/Day 0 if necessary, and at Week 24. During Part 1B and 2, disease activity will be measured by the IgG4-RD RI at Screening, Baseline/Day 0 if necessary, and at Week 48. The IgG4-RD RI does not need to be repeated at Baseline unless there has been a change in Prednisone or other DMARD or if there has been an apparent change in disease activity between Screening and Baseline. The RI will also be measured at any interim visit conducted because of the possibility of recurrent disease or for the purpose of assessing a potential AE.

Imaging required to complete a full IgG4-RD RI assessment will be performed at the Screening visit. Specifically, all participants will undergo either a CT or MRI of the chest, abdomen, and pelvis within 6 weeks of the Screening visit. Participants with clinical evidence of orbital disease will also undergo CT or MRI of that area. If abnormalities in a particular area are detected at Screening, the participant will have the same type of study repeated at Week 24 (Part 1A) or Week 48 (Part 1B and 2) unless there are contraindications to use of the same imaging technique. Imaging at Week 24 (Part 1A) and Week 48 (Part 1B and 2) will be performed if there is a clinical reason to suspect disease activity at that site. Imaging may also be repeated at the discretion of the investigator at a visit other than those two time points if required to assess disease activity because of a potential disease flare or to assess an adverse event. If

participants have received prednisone or another glucocorticoid agent for a total of more than 21 days in the interval between the time of qualifying imaging and the Screening visit, the imaging will be repeated at Screening.

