Adverse Event Assessment		X	X	X	X	X	X	X	X	X	X	X	X	X	X	X
Concomitant Medications	X	X	X	X	X	X	X	X	X	X	X	X	X	X	X	X
SARS-CoV-2 Antigen Test ¹⁷		X			X		X		X		X		X			
Disease Activity Assessments																
CT scan w/ or MRI w/o contrast ^{3, 3a}	X														X	X
IgG4-RD Responder Index (RI) ¹³	X	X ¹⁶													X	X
Physician Global Assessment VAS	X	X		X	X	X	X	X	X	X	X	X	X	X	X	X
Patient Global Assessment VAS	X	X		X	X	X	X	X	X	X	X	X	X	X	X	X
Flare Documentation Guide ¹²	X	X		X	X	X	X	X	X	X	X	X	X	X	X	X
SF-36 Health Survey		X			X		X		X		X		X		X	X
Clinical Laboratory Assessments																
CBC with differential/ANC ^{11, 11a}	X	X		X	X	X	X	X	X	X	X	X	X	X	X	X
Comprehensive Metabolic Panel ^{11, 11a}	X	X		X	X	X	X	X	X	X	X	X	X	X	X	X
Serum amylase and lipase	X	X		X	X	X	X	X	X	X	X	X	X	X	X	X
eGFR ⁴	X	X		X	X	X	X	X	X	X	X	X	X	X	X	X
Serum Immunoglobulins ¹⁵		X			X		X		X		X		X		X	X
Serum IgG subclasses		X			X		X		X		X		X		X	X
ESR		X			X		X		X		X		X		X	X
CRP		X			X		X		X		X		X		X	X
Serum complement: C3 and C4		X			X		X		X		X		X		X	X

Visit Name	Screening	Base-line/ Day 0 ¹	Day 7 (phone call)	Week 4	Week 8	Week 12	Week 16	Week 20	Week 24	Week 28	Week 32	Week 36	Week 40	Week 44	Week 48	Unscheduled ¹⁴
Visit window	-28 days	N/A	±2 days	±7 days	±7 days	±7 days	N/A									
ELF score ⁵		X			X			X		X			X			X
TB Testing ⁶	X															
Clinical Laboratory Assessments (continued)																
Other infectious disease testing ⁷	X															
Urinalysis and culture ⁸	X									X					X	X
Serum HCG ⁹	X															
Urine HCG ⁹		X			X		X		X		X		X			
Mechanistic Assessments																
Flow Cytometry: PBMC collection	X ¹⁸	X ¹⁸			X		X		X		X		X		X	X
Plasma Collection	X ¹⁸	X ¹⁸			X		X		X		X		X		X	X
Submandibular Gland Biopsy ¹⁰	X ¹⁹	X ¹⁹											X ^{10a}	X ^{10a}		
Study Drug Administration																
Elotuzumab/placebo 10 mg/kg IV		X			X		X		X		X		X			
Oral steroid		X		X	X											
Steroid compliance check			X	X	X	X										

¹ Baseline/Day 0 assessments may be split to accommodate submandibular gland biopsy so long as first infusion occurs within 28 days of start of screening.

² Height at screening. At the Baseline/Day 0 visit, the screening weight will be used for calculation of the baseline infusion dose. For all subsequent infusions, the weight assessed at the previous infusion visit will be used for calculation of dose.

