³ Imaging required to complete a full IgG4-RD RI assessment will be performed for the Screening visit. Specifically, all participants will undergo either a CT or MRI of the chest, abdomen, and pelvis at Screening. Participants with clinical evidence of orbital disease will also undergo CT or MRI of that area. If abnormalities in a particular area are detected at Screening, the participant will have the same type of study repeated at Week 48. Imaging at week 48 will be performed if there is a clinical reason to suspect disease activity at that site. Imaging may also be repeated at the discretion of the investigator at a visit other than those two time points if required to assess disease activity because of a potential disease flare or to assess an adverse event.

^{3a} Oral or intravenous contrast agents may be used in some radiology studies. The need for contrast agents will be reviewed on an individual basis, consistent with the routine use of these imaging studies. Consultation with radiology will be obtained as needed.

⁴ eGFR to be calculated centrally per the CKD-EPI formula.

⁵ ELF Score serology: TIMP-1, PIIINP, HA.

⁶ By Interferon-Gamma Release Assay (IGRA) at or within 90 days of the Screening visit. If indeterminate, repeat (with same or other IGRA per local policy) or obtain PPD (the later to be read within 48-72 hours and may be read locally with documentation of result by health care provider). If history of BCG vaccine or other complication in interpretation of result, consultation with ID is required for clearance to proceed.

⁷ HIV, Hepatitis B surface antigen and Hepatitis B core antibody, Hepatitis C antibody.

⁸ U/A macroscopic and microscopic analysis, culture if indicated.

⁹ For women of child-bearing potential. Stat urine HCG prior to each infusion may be performed locally with point of care testing.

¹⁰ Submandibular gland biopsy: fine needle aspiration of parotid or submandibular salivary gland. Sub-study to be conducted only at MGH. May use tissue previously acquired if available. Opt-out language to be included in the informed consent document.

^{10a} Submandibular gland biopsy may be obtained between Week 40 and 44.

¹¹ To be obtained stat locally and reviewed before each infusion (or within 72 hours of subsequent infusion).

^{11a} Safety labs should be repeated at Baseline/Day 0 after screening only as clinically indicated.

¹² To be completed only at visits following a flare occurrence.

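### The synopsis sets RI damage at 24 weeks for both parts, but Parts 1B and 2 schedule no Week 24 RI; Section 3.3 gives no time point

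*Combined protocol and SAP*

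**What the plan says.** Under the additional secondary efficacy endpoints for Part 1 and Part 2, the synopsis has "Disease-related damage, as measured by the damage section of the IgG4-RD RI at 24 weeks". The matching item in Section 3.3 stops earlier, at "Disease-related damage, as measured by the damage section of the IgG4-RD RI", and names no visit. Section 13.2 refers to Sections 3.2 to 3.4 for the endpoints and does not mention the synopsis.

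Section 3.5.2 makes the damage assessment part of the RI and fixes when the RI is done: "During Part 1A, disease activity will be measured by the IgG4-RD RI at Screening, Baseline/Day 0 if necessary, and at Week 24", whereas "During Part 1B and 2, disease activity will be measured by the IgG4-RD RI at Screening, Baseline/Day 0 if necessary, and at Week 48". It adds that "The RI will also be measured at any interim visit conducted because of the possibility of recurrent disease" or to assess a potential adverse event. For Parts 1B and 2, footnote 3 of the Appendix 1 schedule puts the repeat imaging at the same visit: "If abnormalities in a particular area are detected at Screening, the participant will have the same type of study repeated at Week 48".

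Section 13.4.4 reports the number of organ sites with damage by arm and compares the arms with Fisher's exact test. It names neither a visit nor a baseline reference. The RI form in Appendix 3 defines damage as permanent organ dysfunction due to the disease.

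**The concern.** A secondary endpoint should name a visit at which the plan collects the data. In the randomised part, the visit named in the synopsis has no RI, and neither Section 3.3 nor Section 13.4.4 supplies another. The visit for the between-arm damage comparison is therefore not fixed in advance, even though one scheduled visit would serve.

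A lesser matter concerns the variable. Because damage is permanent, an organ already damaged at entry is counted again at follow-up. The comparison then mixes pre-treatment damage, which treatment cannot change, with damage arising during the trial.

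**Working it through.** **Step 1. Where the RI is scheduled.** Planned numbers come from Sections 3.1.1 and 3.1.3: six in Cohort 1a, six in Cohort 1b, 63 in Part 2. RI visits come from Section 3.5.2, checked against the RI rows of the two Appendix 1 tables. The Part 1A row has 14 visit columns, ticked at Screening, Baseline, Week 24 and Unscheduled. The Part 1B and Part 2 row has 16, ticked at Screening, Baseline, Week 48 and Unscheduled. Text and tables agree, so the finding does not depend on how a table was extracted.

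| Part | Planned n | Scheduled post-baseline RI | Participants with a scheduled Week 24 RI | Participants with a scheduled Week 48 RI |
|---|---|---|---|---|
| 1A | 6 | Week 24 | 6 | 0 |
| 1B | 6 | Week 48 | 0 | 6 |
| 2 | 63 | Week 48 | 0 | 63 |
| All | 75 | | 6 (6/75 = 8%) | 69 (69/75 = 92%) |

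These are planned numbers, not expected completers. The randomised comparison has 0 of 63 at Week 24 and 63 of 63 scheduled at Week 48.

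**Step 2. Which text governs.** The synopsis says 24 weeks; Section 3.3 is silent; Section 13.2 points to Section 3.3. The contradiction therefore lies between the synopsis and the RI schedule. Section 3.3 does not contradict the schedule, but it does not settle the visit either.

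**Step 3. The reverse gap.** For both parts, the threshold endpoint in the synopsis and Section 3.3 reads "The proportion of participants that reach the following threshold levels of IgG4-RD RI improvement at 48 weeks: 50% and 75" per cent. The table shows no scheduled Week 48 RI for the six participants in Cohort 1a.

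**Step 4. Effect of counting damage present at entry.** The documents give no damage rates and no power for this endpoint; Section 13.7 covers only the primary endpoint and complete remission. The direction can still be shown for a simplified outcome, any damaged site. Let d be the share entering with damage, the same in expectation in both arms by randomisation. Let q be the probability of new damage, assumed independent of damage at entry, with qP for placebo and qE for elotuzumab. Then

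P(any damaged site) = d + (1 − d)q,

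and the arm difference is [d + (1 − d)qP] − [d + (1 − d)qE] = (1 − d)(qP − qE).

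For assumed d of 0.1, 0.3 and 0.5, the difference is 0.9, 0.7 and 0.5 times the difference in new damage. If qP = qE it is zero for every d, so the test remains valid and only sensitivity is lost. Section 13.4.4 compares numbers of sites rather than any versus none, so these factors show direction only and do not estimate the loss in this trial.

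**The case against.** The strongest reply is that the body of the protocol already leads to Week 48. Section 13.2 takes the endpoints from Section 3.3, which sets no time point, and Week 48 is the only scheduled post-baseline RI in Part 2. On this reading the error is one phrase in the synopsis. Most of this stands, and it limits the consequence. It does not remove the need to edit, because the reader must infer the visit and the synopsis states another.

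A reader might go further and infer that the Part 2 comparison would fall back on unscheduled RIs near Week 24, from participants selected by a suspected flare or an adverse event. The documents do not support that: no section plans to use those RIs for this endpoint.

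A separate Statistical Analysis Plan might also settle the matter. The protocol's references to one, in Sections 13.4.3 and 13.5.2, concern supportive analyses of the primary endpoint and safety reports. Such a plan could name Week 48, but it could not produce Week 24 RIs that are not scheduled.

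Week 48 will not be complete either. Section 11.1 follows Part 2 participants after study drug stops unless consent is withdrawn, and the early-withdrawal visit in Section 11.4 is for safety assessments. Moving the time point gives the endpoint scheduled data; it does not guarantee a score for everyone.

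Finally, the baseline reference is a choice. The planned comparison is valid without it, and the reverse gap concerns six open-label participants with no comparator. Both observations stand.

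**Conclusion.** The synopsis is wrong as written. Its damage endpoint has a scheduled measurement for 6 of 75 planned participants, all in Cohort 1a, and for 0 of 63 in the randomised comparison. This rests only on the stated cohort sizes and RI schedule. It does not mean that Part 2 lacks damage data: the Week 48 RI provides them, and Section 3.3 is compatible with that visit.

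Counting newly damaged sites would be a free improvement rather than the correction of an error. The size of the dilution is unknown, because it depends on damage rates that the documents do not give.

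Section 13.4.4 treats this endpoint as supportive. The primary test, the key secondary test and their type I error are unaffected.

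A reader might also infer from Section 13.4.4 that the analysis of covariance for the physician and patient global assessments omits the baseline score, since only treatment is named. The text does not exclude covariates, and nothing is lost if baseline is intended, so no claim is made on that point.

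**What to change.** 1. In the synopsis and Section 3.3, state RI damage at Week 24 for Part 1A and at Week 48 for Parts 1B and 2.
2. As a minor matching edit, give the 50% and 75% RI thresholds a time point by part, since Part 1A has no scheduled Week 48 RI.
3. As an improvement, define the damage variable in Section 13.4.4 as the number of organ sites newly damaged since the last RI before the first infusion (Screening, or Baseline/Day 0 where repeated), and keep Fisher's exact test.
4. Optionally, reconcile Section 8.2 and footnote 14 of the Part 1B and Part 2 schedule, which send flare visits to the Week 24 assessments, with that schedule: its Week 24 column has no RI or imaging, while its Unscheduled column ticks both.

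The cost is wording. No visits, scans, data items or participants are added, and the new-damage count uses RIs already planned.
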